1. ABSTRACT

Background: Exercise snacks have emerged as a promising strategy to improve physical function in older adults. However, the optimal fragmentation pattern (i.e., how to distribute a fixed daily volume of exercise across the day) remains unknown. Furthermore, the effects of resistance-based exercise snacks on cognitive function in pre-frail older adults have not been investigated.

Objective: To compare the effects of four different fragmentation patterns of a three-exercise resistance snack (sit-to-stand, squat, and heel raise) on lower limb strength, dynamic balance, and executive cognitive function in community-dwelling pre-frail older adults.

Design: Four-arm parallel-group randomized controlled pilot trial.

Participants: 60 community-dwelling pre-frail older adults (Fried Frailty Phenotype score 1-2, aged ≥ 65 years).

Interventions: All groups perform a fixed total daily volume of 15 repetitions per exercise (sit-to-stand, squat, and heel raise), resulting in 45 total repetitions per day. The only difference between groups is the fragmentation pattern:

- G1 (highly fragmented): 1 repetition of each exercise per bout, 15 bouts/day (~30 seconds per bout)
- G2 (moderately fragmented): 3 repetitions of each exercise per bout, 5 bouts/day (~90 seconds per bout)
- G3 (lowly fragmented): 5 repetitions of each exercise per bout, 3 bouts/day

(~2.5 minutes per bout)

- G4 (consecutive control): 15 repetitions of each exercise per bout, 1 bout/day (~7.5 minutes per bout)

The intervention period is 8 weeks.

Outcome Measures: Primary outcomes include lower limb strength (30-second chair stand test) and dynamic balance (Timed Up and Go test). Secondary outcomes include comprehensive physical function (Short Physical Performance Battery), executive function (Stroop Color-Word Test and Trail Making Test), and falls efficacy (modified Falls Efficacy Scale). Feasibility outcomes include adherence, acceptability, and adverse events.

Data Analysis: A 4×3 mixed ANOVA will be used to compare group differences. Effect sizes (Cohen's d , η^2) will be estimated to inform a future definitive randomized controlled trial.

Expected Results: This pilot trial will provide preliminary evidence on the dose-response relationship between exercise snack fragmentation patterns and both physical and cognitive outcomes in pre-frail older adults.

2. INTRODUCTION AND BACKGROUND

2.1 Definition and Epidemiology of Pre-Frailty

Frailty is a geriatric syndrome characterized by multisystem dysregulation leading to reduced physiological reserve and increased vulnerability to stressors. The Fried Frailty Phenotype classifies individuals into three categories: robust (0 criteria), pre-frail (1-2 criteria), and frail (≥ 3 criteria). Pre-frailty is an intermediate state between health and frailty and is potentially reversible.

The prevalence of pre-frailty among community-dwelling older adults in China ranges from 26.8% to 62.8%. Pre-frailty represents a "golden window" for intervention because early identification and targeted intervention can reverse pre-frailty to a robust state or delay its progression to frailty.

2.2 Three Types of Exercise Snacks

According to a 2024 scoping review published in *Sports Medicine*, exercise snacks are classified into three types:

Type	Definition	Characteristics
Structured Exercise Snacking	Planned, short bouts of structured exercise	<5 minutes per bout, ≥2 bouts per day
Snackactivity	Activity pattern aimed at frequently breaking up sedentary time	2-5 minutes, multiple times per day
VILPA	High-intensity activities occurring naturally in daily life	1-2 minutes, vigorous intensity

VILPA requires vigorous intensity and is not suitable for pre-frail older adults due to safety concerns. This study focuses on the structured exercise snacking paradigm while incorporating Snackactivity logic (high-frequency interruption of sedentary behavior) as a theoretical comparator.

2.3 Research Gaps

Although exercise snacks have been demonstrated to be feasible in older adults (adherence rates 81-97%), several research gaps remain:

1. **Optimal dose unknown:** No study has systematically compared different fragmentation patterns
2. **Cognitive effects unexplored:** The effects of exercise snacks on cognitive function have not been investigated
3. **Limited resistance-based evidence:** Existing cognitive studies have exclusively used aerobic-based exercise snacks

2.4 Study Objectives

This study aims to:

1. Compare the effects of four different fragmentation patterns on lower limb function and executive cognitive function in pre-frail older adults
2. Explore the dose-response relationship between fragmentation pattern and intervention effects
3. Determine whether 15 repetitions per day is above, at, or below the minimal effective dose threshold for resistance-based exercise snacks

3. STUDY DESIGN

Design Overview

- **Design:** Four-arm parallel-group randomized controlled pilot trial

- **Allocation Ratio:** 1:1:1:1
- **Masking:** Assessor-blind (outcome assessors unaware of group assignment)
- **Intervention Period:** 8 weeks
- **Assessment Time Points:** Baseline (Week 0), Mid-intervention (Week 4), Post-intervention (Week 8)

4. STUDY POPULATION

4.1 Inclusion Criteria

1. Age 65 years or older
2. Community-dwelling (living independently, not in a nursing home or long-term care facility)
3. Pre-frail status confirmed by Fried Frailty Phenotype score of 1-2
4. Mini-Mental State Examination (MMSE) score ≥ 24
5. Able to walk independently with or without a cane
6. No regular lower limb strength training (less than 2 times per week) in the past 3 months
7. Willing to adhere to the 8-week exercise intervention and complete all assessments
8. Provide written informed consent before any study-related procedures

4.2 Exclusion Criteria

1. Lower limb fracture or joint replacement surgery within the past 6 months
2. Unstable angina or uncontrolled hypertension (resting systolic blood pressure ≥ 160 mmHg)
3. Severe osteoporosis (T-score < -2.5 with history of fragility fracture)
4. Neurological disorders affecting motor function (e.g., Parkinson's disease, post-stroke hemiplegia)
5. Severe cognitive impairment (MMSE score < 24)
6. Unstable cardiac or pulmonary disease (e.g., recent myocardial infarction, severe COPD exacerbation)
7. Severe visual or hearing impairment that limits ability to follow instructions or

perform exercises safely

8. Participation in another interventional clinical trial within the past 30 days
9. Any other medical or psychological condition that, in the opinion of the principal investigator, would compromise participant safety or study adherence

4.3 Sample Size

As a pilot trial, formal power calculation is not performed. Fifteen participants per group (total N=60) will be recruited. Anticipating a 20-25% attrition rate, approximately 45 participants (11-12 per group) are expected to complete the 8-week intervention.

5. INTERVENTION

5.1 Four-Group Design Overview

All groups perform a fixed total daily volume of 15 repetitions per exercise (sit-to-stand, squat, and heel raise), resulting in 45 total repetitions per day. The only difference between groups is the fragmentation pattern.

Group	Repetitions per Bout (per exercise)	Bouts per Day	Duration per Bout	Fragmentation Level
G1 (Highly Fragmented)	1	15	~30 seconds	Highest
G2 (Moderately Fragmented)	3	5	~90 seconds	Moderate
G3 (Lowly Fragmented)	5	3	~2.5 minutes	Lower
G4 (Consecutive Control)	15	1	~7.5 minutes	None

5.2 Exercise Standardization

Sit-to-Stand:

- Starting position: Seated on a rigid chair (seat height 43-45 cm), feet shoulder-width apart, hands crossed over chest
- Movement: Lean forward → extend knees to stand → hold fully upright for 1 second → slowly sit back down
- Progression/regression: Hands on armrests (regression), seat height increase (regression)

Squat:

- Starting position: Standing, feet shoulder-width apart, hands on hips or holding chair back
- Movement: Keep back straight → bend knees and lower hips as if sitting back → thighs parallel to ground → stand up

- Progression/regression: Partial squat (regression), holding chair back (regression)

Heel Raise:

- Starting position: Standing, feet together, hands lightly holding chair back for balance
- Movement: Slowly raise heels to maximum height → hold for 1 second → slowly lower
- Progression/regression: Holding chair back with both hands (regression)

5.3 Triggering Strategies

Group	Trigger Type	Specific Instructions
G1	Event-based	Perform one bout after each bathroom visit and after each time drinking water
G2	Fixed time points	Perform bouts at approximately 9:00, 12:00, 15:00, 18:00, and 21:00
G3	Fixed time points	Perform bouts at morning (9:00), noon (14:00), and evening (19:00)
G4	Fixed time	Perform the single daily bout at a consistent time (e.g., 10:00 AM)

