5.4 Progressive Loading

Phase	Weeks	Strategy
Adaptation	1-2	Slow controlled speed, emphasis on movement quality
Stabilization	3-5	Moderate speed, increase repetitions per bout for G2 and G3
Progression	6-8	Explosive speed (sit-to-stand and squat), optional weighted vest (2-4 kg) for G3 and G4

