6.3 Feasibility Outcomes

Outcome	Definition	Success Criterion
Recruitment Rate	$(\text{Number randomized} \div \text{Number screened eligible}) \times 100\%$	$\geq 60\%$
Retention Rate	$(\text{Number completed 8 weeks} \div \text{Number randomized}) \times 100\%$	$\geq 80\%$
Adherence	$(\text{Actual bouts completed} \div \text{Prescribed bouts}) \times 100\%$	$\geq 80\%$
Acceptability	5-point Likert scale questionnaire	Mean score ≥ 4
Safety	Adverse event rate	No serious adverse events

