9. DATA COLLECTION AND MANAGEMENT

9.1 Data Collection Tools

- **Physical function tests:** 30-second chair stand test, TUG, SPPB
- **Cognitive tests:** Stroop Color-Word Test, Trail Making Test
- **Questionnaires:** FES, IPAQ, Acceptability Questionnaire

- **Process monitoring:** Exercise log, Borg CR-10 scale, video 抽查

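### G1's trigger instruction in section 5.3 does not lead to the 15 bouts a day set in 5.1, and G1 is the only event-triggered arm

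*Protocol*

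**What the plan says.** The abstract and section 5.1 give every arm the same daily total: 15 repetitions of each of three exercises, 45 in all. G1's share is "1 repetition of each exercise per bout, 15 bouts/day". Section 5.1 adds that "The only difference between groups is the fragmentation pattern", and the abstract makes the same claim.

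Section 5.3 then gives each arm its operating instruction. G1, the only arm labelled event-based, is told to "Perform one bout after each bathroom visit and after each time drinking water". The other arms work by the clock. G2, for example, is told to "Perform bouts at approximately 9:00, 12:00, 15:00, 18:00, and 21:00"; G3 has three set times and G4 has one.

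Section 6.3 defines adherence as completed bouts divided by "Prescribed bouts", with 80% as the success criterion. Section 10.1 uses the same 80% to define the per-protocol set. Section 9.1 lists an exercise log among the monitoring tools ("Exercise log, Borg CR-10 scale").

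**The concern.** The trial's premise is equal volume with varied fragmentation. The G1 instruction ties a bout to *each* event, so the number of bouts follows how often a participant drinks and goes to the bathroom. No cap, daily count or make-up rule appears in 5.3 or elsewhere in the protocol. A participant who does as told can end the day above or below 15 bouts.

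There is a second issue, which does not depend on the number of events. Only G1 is cued by events, so a G1 difference cannot be assigned to fragmentation alone.

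G1 is the extreme level of the factor under study. The pairwise comparisons and the trend analysis in 10.2 both use it, and so do the first two objectives in 2.4. The third objective asks where 15 repetitions a day lies relative to a minimal effective dose, which presumes that 15 is the dose each arm is told to perform. The intention-to-treat analysis cannot separate fragmentation from trigger type, or from volume if volume drifts.

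**Working it through.** **Inputs.** Repetitions, bouts and durations come from the table in 5.1, triggers from 5.3, and the 80% threshold from 6.3 and 10.1. Eight weeks is 56 days. The number of trigger events a day, T, is not in the protocol and is treated as unknown.

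**Step 1: reproduce the stated volume and compare it with the triggers.** Volume per exercise is repetitions per bout × bouts per day; the total is three times that.

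| Arm | Per exercise | Total per day | Time per day | Bouts implied by 5.3 |
|---|---|---|---|---|
| G1 | 1 × 15 = 15 | 45 | 15 × 30 s = 7.5 min | T (not stated) |
| G2 | 3 × 5 = 15 | 45 | 5 × 90 s = 7.5 min | 5 |
| G3 | 5 × 3 = 15 | 45 | 3 × 150 s = 7.5 min | 3 |
| G4 | 15 × 1 = 15 | 45 | 1 × 450 s = 7.5 min | 1 |

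The 5.1 table is internally consistent. The triggers in 5.3 reproduce its bout counts in three arms and leave the count open in G1.

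**Step 2: G1 volume under the literal instruction.** One bout is 1 repetition of each of 3 exercises, so daily volume = 3T, and 3T = 45 only when T = 15. Each event away from 15 shifts the volume by 3/45 = 6.7%. Kept up for 56 days, that is 3 × 56 = 168 of 45 × 56 = 2520 repetitions.

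Over an assumed range of T, for illustration only:

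| T | Repetitions per day | Share of 45 |
|---|---|---|
| 8 | 24 | 53% |
| 10 | 30 | 67% |
| 12 | 36 | 80% |
| 15 | 45 | 100% |
| 18 | 54 | 120% |
| 20 | 60 | 133% |

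Section 5.4 does not change G1's bouts or repetitions, so these figures hold for all eight weeks.

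**Step 3: adherence.** Take the prescribed number as 15 a day. A participant who follows every trigger then has adherence T/15. Reaching 80% needs T ≥ 0.80 × 15 = 12. Over the whole period, 15 × 56 = 840 bouts are prescribed, 80% of which is 672, or 672/56 = 12 a day on average. At 11 events a day, full obedience to 5.3 gives 11/15 = 73%. If the prescribed number were instead the count of events, the same participant would score 100%. Both denominators can be read from the text, and they give different answers.

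**Step 4: trigger type.** Set T = 15 for everyone in G1. The volume difference disappears, but G1 is still event-cued while the other three arms are clock-cued. The claim in 5.1 is therefore too absolute whatever T is.

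**The case against.** The strongest reply is that 5.1 sets the dose and 5.3 only supplies cues. Read together, 15 a day governs, events prompt it, and the adherence denominator is already 15. Much of this stands: the protocol does state a target for G1, and it would be wrong to say that none exists. It does not fully answer the point, because 5.3 ties a bout to every event and nothing tells the participant to stop at 15 or to make up a shortfall.

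It can also be said that event cues are a sensible way to deliver 15 short bouts, that this is a pilot, and that whether the cues yield 15 bouts is partly what the adherence outcome measures. That is fair, and the cues need not be abandoned. But the log records departures without preventing them. Low adherence in G1 could also mean either that triggers were ignored or that too few occurred. A separate analysis plan could settle the denominator, but not the participant's instruction.

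A reader might infer that G1 will in fact receive a different volume, or that its comparisons are biased by a known amount. The protocol supports neither, since it gives no T. Nor does G1's place in the contrasts measure bias. It enters 3 of the 6 Tukey pairs, as every arm does. With equal spacing it carries 3/8 = 37.5% of the absolute weight in a linear trend, the same as G4. These figures would be unchanged if 5.3 were perfect.

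**Conclusion.** The point holds as a conflict between an operating instruction and a stated dose, together with an overstated claim about how the arms differ. Under 5.3 as written, G1's volume is 3 repetitions per event and matches the other arms only at 15 events a day. The exact sensitivity is 6.7% per event; the actual deviation and its direction are unknown. The most concrete consequence is for adherence: below an average of 12 events a day, a fully obedient G1 participant misses the 80% threshold used for feasibility and for the per-protocol set. This assumes a denominator of 15 and no bouts beyond those triggered. The confounding of trigger type with G1 needs no assumption about T.

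Section 5.4 also departs from the claim in 5.1, through its plans to "increase repetitions per bout for G2 and G3" and its "optional weighted vest (2-4 kg) for G3 and G4". That is a separate issue, and nothing here rests on it.

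**What to change.** **Section 5.3, G1 row.** Suggested text: *Bathroom visits and drinks of water are prompts toward a daily total of 15 bouts. Stop once 15 are done. If fewer than 15 prompts occur, do the remaining bouts as separate single bouts later the same day where feasible, and log any not done as missed.*

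**Section 6.3.** State that G1's prescribed bouts are 15 a day.

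**Abstract and 5.1.** Replace the claim of a sole difference with, for example: *The arms are designed to differ in fragmentation; G1 also differs from the other arms in trigger type.* Interpret G1 contrasts as fragmentation together with trigger type. The 5.4 differences should be resolved on their own; this wording does not settle them.

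**Cost.** Edits to four places and to the G1 participant instructions, with no new visits, tests or participants. G1 participants must keep a daily count, which the planned log can hold, and may have some catch-up bouts. Those bouts are not event-cued and may fall late in the day, so they slightly alter the spread of bouts in G1. The stop at 15 and the make-up rule together bring G1 to 45 repetitions a day when followed. They do not remove the trigger difference, which is why the 5.1 wording must change as well.

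### The G1 trigger in Section 5.3 has no waking-hours limit, so followed literally it can prompt night-time bouts in pre-frail older adults, in that arm only

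*Protocol*

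**What the plan says.** Section 5.3 defines the G1 trigger by events: "Perform one bout after each bathroom visit and after each time drinking water". The other arms are tied to the clock. G2 is told "Perform bouts at approximately 9:00, 12:00, 15:00, 18:00, and 21:00", G3 is given 9:00, 14:00 and 19:00, and G4 is told "Perform the single daily bout at a consistent time (e.g., 10:00 AM".

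The daily count is set elsewhere. The Abstract gives G1 as "1 repetition of each exercise per bout, 15 bouts/day (~30 seconds per bout", and Section 5.1 states "All groups perform a fixed total daily volume of 15 repetitions per exercise".

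Participants are pre-frail and at least 65 years old, and Section 4.1 admits people who are "Able to walk independently with or without a cane". For the squat, Section 5.2 gives "Starting position: Standing, feet shoulder-width apart, hands on hips or holding chair back". Section 5.4 moves to "Explosive speed (sit-to-stand and squat" in weeks 6-8. Section 11.1 lists falls and dizziness after exercise among the monitored events.

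**The concern.** The G1 rule applies to every bathroom visit and every drink, without qualification. Older adults may get up at night for either reason, and the instruction as written then asks for a bout. Nothing in the exercise standardization (5.2), the progression (5.4) or the safety section (11) limits the hour.

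What is at stake is participant safety in one arm, and the comparability of the safety data between arms. Section 6.3 makes the absence of serious adverse events the safety criterion, and Section 11.2 lists a single serious adverse event under early termination. A serious fall during a night bout would count against both, through a bout that the research question does not need.

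**Working it through.** **Step 1: the dose in 5.1 is consistent.** Repetitions per exercise per day = repetitions per bout × bouts:

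- G1: 1 × 15 = 15
- G2: 3 × 5 = 15
- G3: 5 × 3 = 15
- G4: 15 × 1 = 15

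Over three exercises this gives 15 × 3 = 45, the stated daily total. G1's count is therefore fixed at 15 bouts, each of about 30 seconds.

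**Step 2: does the count also limit the hour?** It does not. A limit of 15 per day blocks a night bout only once 15 have been done. If the day is counted from getting up, a night visit is still a valid trigger whenever fewer than 15 bouts have been completed. If it is counted from midnight, the early hours come at the start of the count, when the limit is unlikely to have been reached. The protocol does not say which applies, and on neither reading are night events excluded.

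**Step 3: which arms are exposed?**

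| Arm | Trigger in 5.3 | Open to the night? |
|---|---|---|
| G1 | bathroom visits and drinks, no hours given | yes |
| G2 | five clock times, 9:00 to about 21:00 | no |
| G3 | three clock times, 9:00 to 19:00 | no |
| G4 | one consistent time, example 10:00 | not by the example given |

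**Step 4: what a night bout contains.** One sit-to-stand, one squat and one heel raise. The heel raise is done holding a chair back. The squat may be done without support. In weeks 6-8 the sit-to-stand and squat are performed at explosive speed.

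**Step 5: size.** This would need the number of night visits or drinks, the share followed by a bout, and the risk per night bout compared with a day bout. The protocol gives none of these, so no figure is offered.

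**Step 6: what a waking-hours limit demands of G1.** The 80% adherence criterion (6.3, also used for the per-protocol set in 10.1) corresponds to 0.80 × 15 = 12 bouts per day. The waking day is not given. Assuming 14 to 17 hours (840 to 1020 minutes):

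- 15 bouts: 840/15 = 56 to 1020/15 = 68 minutes between bouts
- 12 bouts: 840/12 = 70 to 1020/12 = 85 minutes between bouts

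Two assumed cases show the effect on adherence if two night bouts are lost and not made up:

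- from 15 bouts: 13/15 = 86.7%, still above 80%
- from 13 bouts: 13/15 = 86.7% falls to 11/15 = 73.3%, below 80%

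The second case is why the fix needs a make-up rule.

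**The case against.** The strongest reply is that nobody intended night exercise. The Abstract speaks of spreading a set volume over the day, and Section 2.2 gives interruption of sitting time as part of the rationale. Both point to waking hours, and many participants would skip a night bout by common sense. This makes the literal reading less likely to be the intended one. It does not put a limit into the instruction that participants are asked to follow.

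A second reply is that the added risk is not shown. The participant is already out of bed, the bout is short, and Section 5.2 allows armrests, a higher seat, a partial squat and chair support. Explosive speed applies at every hour and is not a hazard of the night as such. Section 11.1 also provides for assessing the cause of a fall and modifying the protocol. All of this stands and limits the weight of the point. However, that last safeguard acts only after a fall.

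A reader might also infer that G1's daily volume is uncapped, because 5.3 does not repeat the 15 bouts. The documents do not support this. The Abstract and 5.1 fix the count, and a table of triggers need not restate it.

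**Conclusion.** The point holds in a limited form. The G1 instruction in 5.3 covers night-time events, no other section excludes them, and 5.1 governs the number of bouts but not the hour. Followed literally, the rule can prompt night-time bouts in pre-frail older adults, in G1 only.

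The conclusion rests on participants taking the wording at face value. A reader might infer that G1 will have more falls or is unsafe as designed. The documents do not show that, because they contain no night-visit rate and no risk by hour. Nor is this a fault in the dose, the comparison of arms or the analysis. It is a change worth considering, because the exposure serves no stated purpose and can be removed at small cost.

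**What to change.** Reword the G1 instruction in 5.3, and the matching participant instruction, along these lines: *after each bathroom visit and each drink between getting up in the morning and going to bed, until the 15 bouts per day in 5.1 are reached; do not exercise after night-time visits; if fewer than 15 triggers occur, do the remaining bouts as separate single bouts spaced through the waking day.* Record bout times in the exercise log already listed in 9.1.

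The cost is one sentence and one extra log entry per bout. Arms, sample size and analysis stay as they are. There are two downsides. Some G1 bouts will be self-prompted rather than event-triggered. Participants close to 12 bouts per day who do not make up lost bouts could drop below the 80% threshold, which the adherence measure in 6.3 would show. The change does not remove the difference in trigger type between G1 and the clock-based arms.
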